The use of this tool has been extensively studied during general anesthesia, demonstrating that monitoring nociception response levels with the NOL Index can help reduce postoperative pain, patient stress hormone levels (ACTH and cortisol) (Meijer, 2020), and intraoperative opioid use, resulting in fewer hypotensive events and associated myocardial and renal damage (Meijer, 2019). Additionally, it has been shown that the combined use of the NOL Index and Bispectral Index during general anesthesia can provide accurate and complementary information to guide optimal administration of analgesic and hypnotic drugs (Meijer, 2020).

The rationale for this study lies in the context of relatively short surgical procedures (lasting between 30 and 90 minutes) requiring deep sedation anesthesia. The hypnotic efficacy of commonly used sedation protocols is widely studied and validated by international scientific literature. It is also important to consider that, in some cases, excessive administration of sedatives with insufficient analgesic coverage may occur, leading to seemingly acceptable postoperative results, while in reality, patients experience painful situations without remembering them. This can be particularly dangerous in fragile patients, where heightened adrenergic system activation leads to serious complications.

Therefore, we ask: "Are our sedation protocols, aside from their hypnotic effectiveness, equally effective at the analgesic level?"

Finally, an ethical question must also be highlighted, as proper pain management, in all its forms, is a duty the clinician must address.

Study Purpose

Evaluate the efficacy of the sedation protocol from a nociceptive perspective through continuous intraoperative nociception monitoring (NOL Index).

Primary Objective

The sedation protocol will be considered nociceptively ineffective if the percentage of time the NOL index exceeds the threshold of 25, relative to the observation time, is greater than 25%.

The NOL Index observation time is defined as the interval between reaching an adequate sedation level (Bispectral Index - BIS between 40 and 60) and the end of surgical stimulation.

Secondary Objectives

1. Time the NOL index exceeds the threshold of 25, expressed in minutes
2. Number of peaks with NOL index above 40
3. Evaluate any correlation between the primary objective and the NRS scale 15 minutes post-operation

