- ASA Physical Status

Clinical Data

- Surgical Procedure performed
- Heart Rate (HR)
- Non-invasive Blood Pressure (NIBP)
- Pulse Oximetry (SpO2)
- Bispectral Index (BIS)
- NOL Index
- NRS Pain Scale

Statistical Analysis

Continuous variables will be presented as mean and standard deviation or as median and interquartile range depending on the distribution. Normal distribution will be assessed using the Kolmogorov-Smirnov test. Any sub-analyses and comparisons between subgroups will be performed using Student's t-test for parametric data, while the Mann-Whitney test will be used for non-parametric data. Categorical variables will be presented as absolute number and percentage relative to the total sample size. Any sub-analyses and comparisons between subgroups will be performed using the chi-square test or Fisher's exact test depending on the subgroup sizes. In all cases, the null hypothesis will be rejected for values of $\alpha < 0.05$. The software used for data analysis and sample sizing is Medcalc v. 22.013 (MedCalc Software, Ostend, Belgium).

Sample Size Determination

Following the manufacturer's indications, a nociceptive response measured at NOL >25 is considered

positive. In the absence of similar studies and reference parameters, we have set, based on clinical experience, a mean $\leq 10\%$ of the observation interval, with NOL ≥ 25 , as not significant for the presence of a nociceptive stimulus (Null Hypothesis). We have also considered a mean $\geq 25\%$ of the observation interval, with NOL ≥ 25 , as significant for the presence of a nociceptive stimulus. By calculating the sample size for a single mean, setting the type I error α to 0.05, power β to 0.8, estimating a standard deviation of 30%, the sample size in the study is determined to be 34 subjects.

Approval from the Competent Authority

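### The 10% and 25% cut-offs and the sample size are set for a mean, but the normality rule, which does not exempt the primary variable, can replace that mean by a median in the report

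*Combined protocol and SAP*

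**What the plan says.** The primary variable is the share of each patient's observation time with NOL above 25. Under Primary Objective, the sedation protocol counts as nociceptively ineffective if the "percentage of time the NOL index exceeds the threshold of 25, relative to the observation time, is greater than 25" per cent. That section does not say whether the 25% applies to a mean, a median or each patient.

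Sample Size Determination is specific. A mean of at most 10% "of the observation interval, with NOL ≥ 25 , as not significant for the presence of a nociceptive stimulus (Null Hypothesis") is one cut-off. A mean of at least 25% "of the observation interval, with NOL ≥ 25 , as significant for the presence of a nociceptive stimulus" is the other. The number of patients follows from these: "By calculating the sample size for a single mean", and "estimating a standard deviation of 30%, the sample size in the study is determined to be 34 subjects".

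Statistical Analysis gives the rule for summaries: "Continuous variables will be presented as mean and standard deviation or as median and interquartile range depending on the distribution". It adds: "Normal distribution will be assessed using the Kolmogorov-Smirnov test". No variable is exempt. The tests it names are for sub-analyses and subgroup comparisons: Student's t-test for parametric data, "while the Mann-Whitney test will be used for non-parametric data", and chi-square or Fisher's exact test for categorical data. It also sets a 0.05 level for rejecting the null hypothesis in all cases.

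**The concern.** The design is built around one quantity, the mean percentage of observation time above the NOL threshold. The only instruction on how to summarise a continuous variable lets the data decide whether that quantity is shown. If the Kolmogorov-Smirnov test rejects normality, mean and SD give way to median and IQR.

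A median and a mean are different quantities when the data are skewed. A reader given only a median could not tell on which side of 10% or 25% the mean fell, so could not apply the study's own cut-offs. For right-skewed data the median lies below the mean, so such a reader might also take the sedation protocol to be analgesically better than the planned criterion would show.

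**Working it through.** **1. Reproduce the plan's figure.** Inputs from Sample Size Determination: null mean 10%, alternative mean 25%, SD 30%, α = 0.05, power 0.8. The text does not state sidedness.

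- Difference: 25 − 10 = 15 points. Standardised effect: 15/30 = 0.5.
- Normal approximation, two-sided: n = ((1.960 + 0.842) × 30/15)² = 31.4, so 32.
- One-sample t-test (noncentral t, noncentrality 0.5√n), two-sided: power is 0.795 at n = 33 and 0.808 at n = 34.

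The smallest n that reaches 0.80 is 34, which matches the plan. The design target is therefore the mean, tested against 10%.

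**2. Is the normality rule likely to trigger?** At mean 25% and SD 30%, zero lies 25/30 = 0.83 SD below the mean. A normal distribution would put Φ(−0.83) = 0.20 of patients below 0%, which is impossible on this scale. At mean 10%, the largest SD possible on 0–100% is √(10 × 90) = 30%, reached only if every patient is at 0% or 100%. The planning values are hard to reconcile with a symmetric, bell-shaped variable.

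**3. How often, and how far apart are mean and median?** The documents give no shape, so a beta distribution on 0–100% is assumed. Its parameters are a = mk and b = (1 − m)k with k = m(1 − m)/s² − 1. For m = 0.25 and s = 0.30, k = 0.1875/0.09 − 1 = 1.083, a = 0.271 and b = 0.813. The plan does not say which Kolmogorov-Smirnov version applies, so both were run at the 5% level with n = 34. The critical distances are 0.2274 (uncorrected) and about 0.150 (Lilliefors, simulated). Each setting had 100,000 simulated studies, except the SD 25% and 15% rejection rates, which come from 4,000.

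| True mean 25% | Population median | Normality rejected: uncorrected | Normality rejected: Lilliefors |
|---|---|---|---|
| SD 30% | 10.2% | 54% | 99% |
| SD 25% | 16.3% | 13% | 85% |
| SD 20% | 20.3% | 2% | 50% |
| SD 15% | 22.6% | 0.4% | 23% |

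At the plan's own SD, a study whose true mean sits on the 25% cut-off would often be summarised by a median near the 10% cut-off.

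**4. Illustration only: if the 25% verdict were read from the displayed median.** The event is: normality rejected, sample mean above 25%, sample median at or below 25%. Only true means above 25% are shown.

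| True mean | SD 30%: uncorrected to Lilliefors | SD 20%: uncorrected to Lilliefors |
|---|---|---|
| 30% | 10% to 56% | 0.3% to 15% |
| 35% | 3% to 33% | 0.05% to 3% |

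The opposite event (mean at or below 25%, median above) occurred in at most 0.08% of studies in these beta settings. Other shapes could behave differently.

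**The case against.** The strongest reply is that the quoted sentence is about presentation. It does not touch the hypothesis, the test or the verdict, and it does not forbid giving the mean as well. Sample Size Determination already states a null for the mean (at most 10%), and Statistical Analysis gives a 0.05 rejection level, so the natural reading is a one-sample test of the mean that no display rule alters. All of this stands.

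A reader might infer something stronger: that the plan switches its verdict from the mean to the median, so that a set share of studies would reach the wrong conclusion. The documents do not support that, because no sentence ties the verdict to the displayed summary. The rates in step 4 of the working need that extra step, which is why they are only an illustration. Nor would every shift towards effective be an error: at a true mean of 25% or below, the criterion of more than 25% is not met, so effective is the right answer there.

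A second reply is that 25% may be a per-patient criterion. Secondary objectives 3 to 5 correlate the primary objective with pain scores and rescue need, which uses it at patient level. If so, the result is a count and a percentage, and the normality rule does not affect it. That is a fair reading of the objective, but the cut-offs in Sample Size Determination are explicitly means.

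What survives is narrower. The only stated instruction for summarising the primary variable can remove from the report the quantity that the cut-offs refer to.

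**Conclusion.** The point holds as a conflict within the plan between the target of the design (a mean) and the rule for reporting it (mean or median, chosen by a normality test). Under an assumed beta shape at mean 25% and SD 30%, the rule would trigger in about 54% to 99% of studies of 34 patients, with a population median of about 10%. At SD 20% the rate falls to 2% to 50%. The range reflects the unspecified version of the test.

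The consequence is a report that may lack the figure needed to apply its own cut-offs. It is not an invalid test or a wrong sample size: N = 34 is reproduced and the stated null is unaffected. The size of the gap between mean and median depends on the shape and SD, which the documents do not settle. The change should be made, and confidence is medium.

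**What to change.** Add to Statistical Analysis: *The primary variable is exempt from the normality rule. The arithmetic mean of the per-patient percentages is always reported with a 95% confidence interval, and the 10% and 25% cut-offs are applied to this mean. Median and IQR are supplementary.*

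If the sponsor instead intends a per-patient verdict at 25%, the plan should say so and report the number and proportion of patients above 25%.

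The cost is a short addition to the text and a little extra reporting. No new data are needed, and N stays at 34.

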4. Evaluate any correlation between the primary objective and the NRS scale 2 hours post-operation
5. Evaluate any correlation between the primary objective and the need for rescue analgesic doses

requested by the patient.

Study Design

Prospective observational clinical study, non-profit, non-pharmacological, utilizing the medical device PMD-200™ (Medasense Biometrics Ltd), in patients undergoing short-duration (less than 90 minutes) and particularly painful surgical procedures, with an indication for deep sedation anesthesia.

Materials and Methods

Eligibility Criteria

Inclusion Criteria

- ✓ Adult patients (>18 years old)
- ✓ ASA Physical Status I - II - III

Exclusion Criteria

- ✗ ASA Physical Status IV
- ✗ Pregnant or lactating patients
- ✗ Pre-existing cardiac arrhythmias
- ✗ Patients with neuromuscular diseases
- ✗ Patients with psychiatric syndromes under pharmacological treatment
- ✗ Patients with chronic continuous use of analgesics
- ✗ Patients with a history of drug abuse
- ✗ Allergy to one or more active ingredients used in the protocol
- ✗ Refusal of consent

Study Population

The study population consists of patients admitted to the "Ss. Trinità of Borgomanero" hospital between March 1, 2024, and August 31, 2024, who need to undergo surgical procedures lasting less than 90 minutes and particularly painful, with an indication for deep sedation anesthesia.

Study Flow-chart

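### The 0.05 rejection rule covers every test, including an unlisted and unlimited set of sub-analyses, with no multiplicity control and no exploratory label

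*Combined protocol and SAP*

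**What the plan says.** The Statistical Analysis section gives test choices for subgroup work and then one threshold for everything. For continuous data: "Any sub-analyses and comparisons between subgroups will be performed using Student's t-test for parametric data", with Mann-Whitney as the non-parametric alternative. A parallel sentence allows any sub-analysis of categorical data by chi-square or Fisher's exact test. The rule that follows is "In all cases, the null hypothesis will be rejected for values of" alpha below 0.05. No subgroup variable is named and no number of comparisons is given.

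The objectives are one primary objective, two descriptive NOL measures (minutes above 25, number of peaks above 40) and three association objectives. The associations relate the primary measure to NRS at 15 minutes, to NRS at 2 hours, and to rescue analgesia: "Evaluate any correlation between the primary objective and the need for rescue analgesic doses".

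Sample Size Determination rests on one comparison, a single mean of 10% against 25% of the observation interval, "setting the type I error α to 0.05" and "power β to 0.8" (power 0.80 is evidently meant), giving 34 subjects.

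**The concern.** A rule that rejects at 0.05 in every case, joined to an open permission to compare any subgroups, lets a comparison chosen after seeing the data be declared significant under the plan as written. The data collection list includes gender, age, weight, height, BMI, ASA status and surgical procedure, and any of these could become a grouping factor.

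The statements at risk are the ones readers may remember: that intraoperative NOL tracks postoperative pain, or that the sedation regimen performs worse in some type of patient or procedure. If such a result comes from an unreported number of looks, its p-value does not carry the 5% error rate it appears to carry. The primary result is not affected.

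**Working it through.** **Inputs.** From Statistical Analysis: 0.05 for each test, no adjustment. From the objectives: one primary and three associations, hence four tests. From Sample Size Determination: null mean 10%, alternative 25% (difference 15 points), SD 30 points, power 0.80, N = 34. The documents give neither the correlation between test statistics nor the number of sub-analyses. Both are assumed below and shown as ranges.

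**1. The plan's own figure.** Normal approximation, two-sided: n = [SD × (z₀.₉₇₅ + z₀.₈₀) / difference]² = [30 × (1.960 + 0.842) / 15]² = 31.4, so 32. The exact noncentral t calculation, two-sided, gives 34 with power 0.808. One-sided versions give 25 (normal) and 27 (t). The stated 34 is therefore reproduced by a two-sided one-sample t-test at 0.05, with the whole 0.05 spent on the primary comparison.

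**2. Named tests, independent, all nulls true.** The chance of at least one false positive in k tests is 1 − 0.95ᵏ.

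- Primary alone: 0.05
- Three associations: 1 − 0.95³ = 0.143
- Primary plus three associations: 1 − 0.95⁴ = 0.185

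Whatever the dependence, the four-test figure cannot exceed 4 × 0.05 = 0.20.

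**3. Named tests, correlated.** The three associations share one NOL measure, and their outcomes are likely to move together. Let f₃ be the chance that at least one of three standard normal statistics with common correlation ρ exceeds 1.96 in absolute value (200,000 simulated draws). Treating the primary test as independent of them, the four-test figure is 1 − (1 − f₃) × 0.95.

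| ρ (assumed) | f₃ | four tests |
|---|---|---|
| 0 | 0.1424 | 0.1853 |
| 0.3 | 0.1353 | 0.1785 |
| 0.5 | 0.1247 | 0.1685 |
| 0.7 | 0.1084 | 0.1530 |
| 0.9 | 0.0844 | 0.1301 |

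**4. Adding unlisted sub-analyses.** The number is assumed and the tests are taken as independent.

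| sub-analyses added | total tests | 1 − 0.95ᵏ |
|---|---|---|
| 4 | 8 | 0.337 |
| 6 | 10 | 0.401 |
| 9 | 13 | 0.487 |
| 10 | 14 | 0.512 |
| 16 | 20 | 0.642 |

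The figure passes one half only at 14 independent tests, that is, ten sub-analyses beyond the four named.

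**5. Effect of remedies on the primary test.** Bonferroni over all four named tests (0.05/4 = 0.0125) would cut primary power at N = 34 from 0.808 to 0.610, and 48 patients would be needed for 0.80. Keeping the primary test at 0.05 and treating the rest as exploratory, or correcting only the three associations, leaves N = 34 unchanged.

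**The case against.** The strongest reply is that this is a small, single-group, non-interventional study, planned without comparable earlier studies, and that formal multiplicity control of secondary questions is not expected in such work. That is fair as far as correction goes, and it is why no correction is required here. It does not excuse the missing label: the plan does not call these analyses exploratory but prescribes rejection at 0.05 throughout.

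A second reply is that the plan already has a hierarchy. The objectives separate primary from secondary, and the study is sized on the primary comparison alone. This stands. A reader might infer that a subgroup finding has equal rank with the primary test, but a shared threshold does not make it so.

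Third, the sentence with the rule closes a paragraph that names only subgroup tests. No correlation coefficient and no one-sample test appear there, so applying the rule to the primary test and objectives 3 to 5 is an inference. It is the natural reading, since no other decision threshold for them is given. On the narrower reading the sub-analyses remain uncontrolled, and the associations have no decision rule at all.

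Finally, a reader might infer that a false positive is likely, for example 1 − 0.95¹⁵ = 54% with fifteen tests. The documents do not support that. Twelve of those fifteen would be invented (three NOL measures over four factors). The NOL measures come from the same trace, so independence would fail. Nor does the sample of 34 cause the problem: family-wise error depends on the number and correlation of the tests, while sample size governs power.

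**Conclusion.** The point holds in a limited form. The plan applies 0.05 to all tests, including sub-analyses of unstated number, and offers neither multiplicity control nor an exploratory label. For the four tests that the plan names or implies, the chance of at least one false positive is about 18.5% under independence and about 13% to 18% for assumed correlations of 0.9 to 0.3 among the three association tests. All these figures take every null as true and each test at exactly 0.05. Beyond those four tests the risk grows with each unlisted comparison. It is uncontrolled rather than shown to be high, because the documents do not say how many comparisons there will be. The primary test at 0.05 is sound on this point and needs no adjustment.

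**What to change.** In Statistical Analysis, replace the sentence containing the rule by:

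> *The 0.05 significance rule applies to the primary analysis only. The association objectives (3-5) and all sub-analyses are exploratory, reported as estimates with 95% confidence intervals and the number of comparisons made, without claims of significance.*

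For this to work, the same section should say which test is the primary analysis. At present it can only be inferred from the sample-size paragraph.

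If the investigators want confirmatory claims from objectives 3 to 5, Holm's correction across those three at family-wise 0.05 is an option, not a requirement. Its first step is 0.05/3 = 0.0167. As a guide, for a Pearson correlation (which the plan does not specify) the value detectable with 80% power at N = 34 would rise from tanh[(1.960 + 0.842)/√31] = 0.465 to tanh[(2.394 + 0.842)/√31] = about 0.52.

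The change needs no extra patients or data, and N = 34 is unchanged. The downside is that some secondary or subgroup results can no longer be called significant.

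### The plan asks whether the regimen is analgesically effective, but defines only ineffective, makes the favourable state the null, and has no outcome for results between its two levels

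*Combined protocol and SAP*

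**What the plan says.** The background section of the protocol poses the research question: "Are our sedation protocols, aside from their hypnotic effectiveness, equally effective at the analgesic level". Study Purpose repeats the aim: "Evaluate the efficacy of the sedation protocol from a nociceptive perspective through continuous intraoperative nociception monitoring (NOL Index".

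The Primary Objective holds the only verdict rule: "The sedation protocol will be considered nociceptively ineffective if the percentage of time the NOL index exceeds the threshold of 25" for more than 25% of the observation time. There is no matching rule for effective. The section also does not say whether the 25% applies to each patient or to the cohort mean.

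Sample Size Determination sets two levels for the mean percentage of time. A mean of 10% or less is described "as not significant for the presence of a nociceptive stimulus (Null Hypothesis"). A mean of 25% or more is taken "as significant for the presence of a nociceptive stimulus. By calculating the sample size for a single mean". The remaining inputs are "setting the type I error α to 0.05, power β to 0.8" and, in percentage points, "estimating a standard deviation of 30". The result: "the sample size in the study is determined to be 34 subjects".

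Statistical Analysis adds a general rule for rejecting null hypotheses at 0.05. It names no test for the primary single-mean comparison, and does not say what non-rejection means or how a mean between 10% and 25% is to be read.

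**The concern.** A test whose null is the favourable state can show that the regimen fails, but not that it works. Keeping the null may mean that nociception is low, or only that 34 patients were too few to tell. A point estimate of 25% or less has the same weakness, because the true mean may still lie above 25%.

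The background section warns that sedated patients may undergo painful stimulation that they do not remember, with danger for fragile patients. False reassurance is therefore an error that matters to this study, and the plan sets no limit on it. A result between the two levels would have to be interpreted after the data are seen.

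**Working it through.** **Inputs** (Sample Size Determination): null mean 10%, alternative mean 25%, difference 15 points, SD 30 points, α 0.05, power 0.80, n = 34. The plan does not state whether α is one- or two-sided.

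**Reproducing 34.** The normal approximation, two-sided, is n = (SD × (1.960 + 0.842) / 15)² = (30 × 2.802 / 15)² = 31.4, rounded up to 32. The two-sided one-sample t-test (noncentral t) gives exactly 34, with power 0.808. One-sided versions give 25 (normal) or 27 (t). So 34 is correct for a two-sided t-test, which is used below.

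**Precision at n = 34, SD 30.**
- SE = 30 / √34 = 5.145.
- t(0.975, 33 df) = 2.0345, so the half-width of the 95% interval is 2.0345 × 5.145 = 10.47 points.
- The 10% null is rejected upward only if the observed mean exceeds 10 + 10.47 = 20.5%.

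**An intermediate result.** Take an observed mean of 18%.
- t = (18 − 10) / 5.145 = 1.555, p = 0.13: the null is kept.
- 18% is not above 25%, so the Primary Objective's rule does not call the regimen ineffective.
- The 95% interval is 18 ± 10.47 = 7.5% to 28.5%. It contains 25%, the plan's own level for significant nociception.

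Neither of the plan's criteria flags this result, and the data do not exclude the unfavourable state.

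**Probability that the 10% null is kept** (noncentral t, n = 34, SD 30):

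| True mean | Null kept |
|---|---|
| 15% | 0.85 |
| 17.5% | 0.71 |
| 20% | 0.53 |
| 25% | 0.19 |

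Under this test imprecision helps the regimen. At a true mean of 25%, the 0.19 becomes 0.44 if the SD is 40, or if only 20 patients are analysed.

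**The Primary Objective's rule read as a point estimate of the cohort mean.** A regimen with a true mean of 25% escapes the ineffective label with probability 0.50; one at 20% escapes with probability 0.83 (normal approximation).

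**What a confidence-limit rule would do.** Excluding 25% requires an upper 95% limit below 25%, that is, an observed mean below 25 − 10.47 = 14.5% at SD 30. Power at n = 34:

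| True mean | SD | Model | Power to exclude 25% |
|---|---|---|---|
| 10% | 30 | normal theory | 0.81 |
| 10% | 30 | exact, values 0 or 100 only | 0.75 |
| 10% | 29 | beta, simulated | 0.76 |
| 10% | 20 | beta, simulated | 0.94 |
| 15% | 30 | normal theory | 0.47 |
| 20% | 30 | normal theory | 0.15 |

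The second row is needed because, on a 0–100 scale with mean 10, the SD cannot exceed √(10 × 90) = 30, and it reaches 30 only if every patient is at 0 or 100. The 0.81 is therefore a normal-theory figure.

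At a true mean of 25%, the nominal chance of wrongly excluding 25% is 2.5%. With skewed (beta-shaped) data it is about 4–5%.

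**The case against.** The strongest counter-argument is that the harm is inferred. A reader might conclude that an imprecise or intermediate result passes as effective by default, or will be reported as showing no significant nociception. No section says so: the plan states when the regimen is ineffective and is silent otherwise. That limit stands. What the documents support is a missing interpretation rule, not a documented wrong one.

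A reader might also infer that more noise always favours the regimen. That holds for the 10% test only. Under the point-estimate rule with a true mean below 25%, noise works the other way: at a true mean of 20% and n = 34, the chance of an observed mean above 25% is 0.03 at SD 15, 0.17 at SD 30 and 0.23 at SD 40.

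Nor does it follow that the study cannot answer its question. Where the mean and SD are reported, an interval can be derived and read. But Statistical Analysis lets the summary be a median and interquartile range if the distribution is not normal, and then no such interval follows.

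Two further objections bear on the remedy. If the 25% criterion applies per patient, it classifies individuals, and an interval for the cohort mean does not complete it; the reading has to be stated. And using 25% as the only margin can sit awkwardly with the 10% level: an observed mean of 17.5% with SD 15 has an interval of 12.3% to 22.7%, which excludes 25% but also rejects the 10% null. The fix below deals with both.

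Finally, this is a small, single-arm observational study. That lowers the severity. It does not remove the point, because the plan sets a null hypothesis, an α, a power and a verdict.

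**Conclusion.** The concern holds as a missing rule of interpretation. The question is about effectiveness, the only verdict defined is ineffective, the null is the favourable state, and no outcome is assigned between 10% and 25%. Neither keeping the 10% null nor a point estimate of 25% or less is evidence of effectiveness. The gap is wide: an observed mean anywhere from 14.5% to 20.5% at SD 30 keeps the null while its interval contains 25%.

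The sample size is not in error: 34 reproduces, and by symmetry it gives the same normal-theory power (0.81) for excluding 25% at a true mean of 10%.

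These figures assume a two-sided α, SD 30 unless stated otherwise, an approximately normal mean except where exact or beta results are given, and the 25% criterion applied to the cohort mean. Severity: should be fixed before analysis.

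**What to change.** Amend the Primary Objective, and refer to it in Statistical Analysis, to say that:

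- The criterion applies to the cohort mean percentage of observation time above the NOL threshold. That mean is reported with its two-sided 95% confidence interval, whatever other summaries are given.
- **Upper limit below 25%:** nociception at the plan's significant level is excluded, which supports effectiveness. If the lower limit is also above 10%, the report says that the mean still exceeds the plan's not-significant level.
- **Lower limit above 25%:** ineffective.
- **Interval containing 25%:** inconclusive.
- Failure to reject the 10% null is not evidence of effectiveness.

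The cost is a few sentences and no extra patients. The downsides should be stated in the plan. Inconclusive results will be common if the true mean is 15% to 20%, given the low power there. The false-effective rate at a true mean of 25% may be about 4–5% with skewed data. An ineffective verdict will also need more than a point estimate above 25%: at SD 30, an observed mean above 25 + 10.47 = 35.5%.
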